7.0 LONGITUDINAL FOLLOW-UP

7.1 Post-Restoration Follow-up Evaluations (12-months and 24-months after implant placement)

Participants will return to the clinic at 12 and 24 months following implant placement. Evaluation of implant function and surrounding tissue health will be determined based on an interview with the participant, clinical examination of the study sites and an analysis of radiographic and photographic data.

At each visit, study personnel will review and update the participant's health history and record any adverse experiences; a study dentist will complete a thorough periodontal evaluation of the implant area and provide an assessment of the prosthetic attachment interface. A set of standardized periapical radiographs and clinical photographs will be made.

Case report forms will be used to record the following observations for each implant site:

- Overall soft tissue health
- Plaque and gingivitis scores (modified Löe and Sillness)
- Pocket depth and clinical attachment level
- Implant Stability
- Retention and stability of prosthetic attachment
- Overall aesthetics (soft tissue contours)
- Assessment of reported pain
- Implant survival

Each participant will complete a patient satisfaction questionnaire. Participants will be asked to report their own assessments for the following criteria:

- Comfort
- Speech
- Appearance
- Ability to taste food
- Ability to chew food
- Pain on mastication
- General satisfaction

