10.2 Implant Survival

At each follow-up evaluation participants will be interviewed to determine if any pain or numbness has been experienced since implant placement or has developed since the previous interview. The implant sites will be examined for any evidence of implant failure including implant suppuration and erythema.

If signs or symptoms of implant failure are observed at any time during the course of the study, a periapical radiograph will be obtained and inspected for signs of radiolucency. The investigator will make assessment of implant status and if a failure is determined, will be reported on the appropriate CRF. At the investigator's discretion a medical and/or surgical attempt to rescue the implant may be made.

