12.3 Outcome Endpoints

The primary efficacy parameter for implant success will be the duration of implant survival from surgical placement to 24 months post-placement across all groups. Measurement of bone height along the implant mesial and distal surfaces at 12 and 24 month follow-up evaluations will be captured from radiographic images and compared to same measurements at insertion. These measurements will be used to derive changes from baseline values.

Efficacy endpoints will include implant and prosthesis function as assessed by gingival health, bone levels and participant subjective satisfaction with the study therapy. Differences between groups will be calculated and used to determine if osseous changes and implant function are different across extraction groups and between implant groups.

Safety will be evaluated by clinical signs and symptoms of dental and medical events.

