This SA will be addressed using a survival analysis approach. The primary outcome measure will be presence of signs and symptoms of infection at the implant site, since implant failure is expected to be rare to non-existent. Frequencies of occurrence of infection will be tabulated for each implant type.

Cox proportional hazards regression will be used to evaluate the rates of infection for LTT and RBT implants, allowing for adjustment for potential confounding variables and covariates. A blocking variable representing the individual subject will be included in order to reflect multiple implants per study subject.

SA-8: Assess peri-implant soft tissue healing adjacent to LTT and RBT surfaced implants

The JEMPT index will be evaluated at the time of final restoration and at 12 and 24 months follow-up evaluations. Mixed model ANOVA will be used to compare changes over time between implant types. The statistical test that will be of primary interest is the implant type by time interaction.

SA-9: Assess changes in the longitudinal crestal bone levels across extraction groups and between implant groups at 12 and 24 months after surgical placement.

The analysis for the SA will be mixed-model ANOVA, accounting for multiple observations per subject. The statistical test that will be of primary interest is the F-test for surface type by time interaction.

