A conservative approach to power estimation was used, assuming an effective sample size of 25 observations per extraction-implant group. Power calculations utilized the Power and Precision, release 2.00, (Borenstein, 2000) and nQuery Advisor 6.0 (Janet D. Elashoff, 1995-2005) software packages. Power to detect a “medium” effect size, corresponding to a difference between group means equal to 0.50 times the within-group standard deviation (sd) was calculated. Also, the effect size detectable with 80% power was calculated. All power estimates were based on two-sided testing at the 95% confidence level.

The power for SA-1 is largely determined by the size of control group, since the primary comparison is equivalent to a t-test of the mean of the controls vs others. Thus, the assumed effective sample sizes of 25 and 75 would yield approximatey 57% power to detect a medium effect size. The difference detectable with 80% power would be approximately 0.65sd .

Power for SA-2, SA-4 and SA-5 was based on a one-way ANOVA model. The proposed sample size would provide 52% power to detect a medium effect size or 80% power to detect an effect size equivalent to a two-group difference of 0.34sd . These approximations also apply to SA-3, with the appropriate sd being the within-group standard deviation of the changes across the observation times.

The total sample size for SA-5 would be 80, or 20 per group, since this SA is based on histology, with a single extraction per participant. Power to detect a medium effect size would be 42%. The effect size detectable with 80% power is equivalent to a two-group difference of 0.72sd.

Power for SA-6 was based on linear regression with a four-category dummy variable. If stability and group each explain 10% of the observed variance, the proposed sample size would provide 80% power to detect an increment of 8.6% in explained variance for the stability*group interaction.

Power for comparison of rates of infection signs for SA-7 was based on the chi-square test for the odds ratio. The proportions in the two groups were centered on 0.50, in order to provide a conservative estimate of power. The effective sample size of 50 per group would provide 80% power to detect an odds ratio of approximately 3.2 for the association between implant type and infection.

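### Sections 12.3 and SA-7 name different primary implant outcomes, neither is the crestal bone of Hypothesis III, and SA-7's infection outcome has no visible dedicated per-implant item

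*Combined protocol and SAP*

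**What the plan says.** Three sections speak to what decides the implant comparison.

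- **Section 12.3:** "The primary efficacy parameter for implant success will be the duration of implant survival from surgical placement to 24 months post-placement across all groups". The same paragraph adds mesial and distal bone height at 12 and 24 months as change from insertion. It does not mention infection.
- **Section 12.4, SA-7:** "The primary outcome measure will be presence of signs and symptoms of infection at the implant site", because failure is "since implant failure is expected to be rare to non-existent". The model follows: "Cox proportional hazards regression will be used to evaluate the rates of infection for LTT and RBT implants", with a blocking term for the participant.
- **Hypothesis III (Section 2.3, repeated in 12.4):** the LTT collar is expected to preserve crestal bone better than the RBT collar. SA-9 analyses that outcome.

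Four places bear on how infection would be recorded.

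- **Section 7.1,** for the 12- and 24-month visits: "Case report forms will be used to record the following observations for each implant site". Eight items follow: soft tissue health, plaque and gingivitis scores, pocket depth with attachment level, implant stability, the prosthetic attachment, aesthetics, pain, and survival.
- **Section 10.2** has the sites examined at each follow-up for signs of failure, with suppuration and erythema as examples. On recording it says: "The investigator will make assessment of implant status and if a failure is determined, will be reported on the appropriate CRF".
- **Section 9.1 and Tables 2 and 3:** adverse events are asked about by interview and recorded from V-2 to V-12, with onset, duration and severity assessed.
- **Section 13.2** says in general terms that study dental data go onto paper case report forms.

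**The concern.** Two results carry a primary label for the implants, and a third outcome is the one that the hypothesis names. If survival shows no difference, infection shows one, and crestal bone shows another or none, nothing in the plan says which is the answer on LTT against RBT. That choice could then be made after the data are seen.

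The outcome that SA-7 puts in place of survival also lacks a stated source. A Cox model needs, for each implant, an event status and a time. The text gives no definition of an infection event, no rule that turns the soft-tissue, gingivitis or pain items into one, and no per-implant onset date. Signs that the examiner sees but the participant does not mention have no stated destination unless the implant is judged to have failed. A missing entry could then be analysed as absence of infection.

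**Working it through.** **1. The plan's own SA-7 figure.** Section 12.5 gives 80% power for an odds ratio of about 3.2, with an effective 50 per group and proportions centred on 0.50. On sidedness it says: "All power estimates were based on two-sided testing at the 95% confidence level". The higher proportion is √3.2/(1+√3.2) = 1.789/2.789 = 0.641 and the lower is 0.359, a difference of 0.283. The standard error is √(2×0.25/50) = 0.100 under no difference and √(2×0.359×0.641/50) = 0.0959 under the alternative. Then z = (0.283 − 1.96×0.100)/0.0959 ≈ 0.906, and power is 82%. The figure reproduces. It is not in dispute and plays no further part here.

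**2. Outcome, analysis and sample size side by side.**

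| Outcome | Label | Analysis in 12.4 | Sample size in 12.5 |
|---|---|---|---|
| Implant survival | primary efficacy parameter (12.3) | none stated; SA-7 applies its survival methods to infection | none |
| Infection signs | primary within SA-7 (12.4) | Cox model | odds ratio about 3.2 |
| Crestal bone | subject of Hypothesis III | SA-9, mixed model, surface type by time | 0.565 sd at 80% power |

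Section 12.5 also lists a bone height comparison under SA-7, which the SA-7 text in 12.4 does not contain. SA-7 thus has two power statements for two different outcomes.

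**3. Can survival separate the collars?** The plan gives no failure rate, so I assume none. Take the case most favourable to a difference: all k failures in one arm, n = 50 per group, implants treated as independent. The two-sided Fisher probability is 2·C(50,k)/C(100,k).

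- k = 5: 2 × 2,118,760 / 75,287,520 = 0.056
- k = 6: 2 × 15,890,700 / 1,192,052,400 = 0.027

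At least six failures, all in one arm, would be needed. That does not fit an event described as "since implant failure is expected to be rare to non-existent". Fisher's test stands in here for a survival comparison and serves only to show scale.

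**4. Where infection could be recorded.**

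| Place | Per implant? | Infection named? | Onset date? |
|---|---|---|---|
| 7.1 list (eight items) | yes | no; soft tissue, gingivitis and pain are indirect | no |
| Tables 2 and 3 (21 and 9 rows) | no | no | no |
| 10.2 examination | yes | suppuration and erythema, as evidence of failure | not stated; form entry named for a determined failure |
| 9.1 adverse events | not stated | if reported | yes |

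No single place gives all three, and no sentence names any of them as SA-7's source.

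**The case against.** **Different levels.** Section 12.3 speaks of implant success, and SA-7 sets an outcome within one aim and gives its reason. The two could be a trial-level and an aim-level outcome. That is a possible reading, but the documents do not adopt it. It would also leave at trial level an outcome that the plan itself expects to have almost no events.

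**Infection can be recorded.** A reader might infer that infection is recorded only when an implant has failed. The documents do not support that. Section 10.2 says where a failure is reported; it does not say that other findings go unrecorded. Adverse events are taken at every visit from V-2 to V-12. The soft-tissue, gingivitis and pain items in 7.1 do not depend on failure, and Section 13.2 makes case report forms the general vehicle for dental data. Section 10.3 counts freedom from persistent infection as part of implant success. The tables are also incomplete as a list of what is recorded: gingivitis scores and implant stability have no row, yet 7.1 puts them on the forms. The forms and the Manual of Procedures (Appendix E) are not in the text and may contain an infection field. All of this stands. What remains is that no dedicated, defined item is visible and no source is named.

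**Arm attribution.** A reader might infer that, in participants with several sites, an infection could not be assigned to LTT or RBT. Section 4.4 rules this out: all study sites in a participant receive the same implant design. Only attribution to a particular implant, which the per-implant Cox model uses, is uncertain.

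**Power.** A reader might infer that SA-7 is underpowered because infections will be under-recorded. The plan gives no infection rate, so any such figure rests on an assumed one. A lower rate would reduce power equally with perfect recording, so it does not measure this defect.

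**Conclusion.** The point holds in two parts, and both should be fixed.

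First, 12.3 and SA-7 name different primary implant outcomes, and neither is the crestal bone of Hypothesis III. By SA-7's own statement, the 12.3 parameter cannot be expected to discriminate between the collars. It has no stated analysis or sample size, and no sentence says which result decides. This rests on the text alone.

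Second, no defined, per-implant infection item with an onset date is visible for SA-7. The Cox model would draw on interview-based adverse event reports and indirect items. This is a gap in specification and not proof that infections go unrecorded. The number of infections that might be missed cannot be estimated from the documents. Confidence is moderate because the forms and the Manual of Procedures are not available.

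**What to change.** 1. **Make 12.3 and SA-7 agree.** Report implant survival descriptively and name one primary implant outcome. Crestal bone change from insertion is what Hypothesis III states. It is already measured on the scheduled radiographs (Section 8.2), analysed in SA-9 and given a sample size statement in 12.5. Change the primary label in SA-7 to match, and correct 12.5 so that the bone height comparison sits under the aim that analyses it.

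2. **If infection is kept as the SA-7 outcome, define it and name its source.** At each follow-up evaluation where 10.2 already requires the site examination, record for each implant whether infection signs or symptoms are present, which ones, and the date of onset, whether or not failure is declared. State that this item supplies the events and times for the Cox model. If the forms already hold such a field, a sentence citing it is enough.

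The cost is slightly more data entry and a few changes of wording in 12.3, SA-7 and 12.5. No new visit, examination or radiograph is needed.

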4.2 Randomization

Participants will be stratified for smoking status and randomized to one of four extraction groups; three experimental groups utilizing three different bone grafting applications and a control group where extraction sockets will be allowed to heal naturally. A secondary randomization will be conducted to select one tooth site per subject to receive trephine sampling for histology evaluation. At the time of enrollment, each participant in groups 1-4 will be further randomized into one of two implant strata.

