4.4 Randomized Implant Groups

Each subject will receive two-stage dental implants with the same overall design features with two different surface treatments at the implant collar. Subjects with multiple sites will receive the same implant design in all study sites.

Group-A: Laser Thread Texturing (LTT) collar surface topography

Group-B: Resorbable Blast Texturing (RBT) collar surface topography

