5.2 Surgical Implant Placement

The implants utilized are identical with the exception of the collar surface characteristics (Table 4). Each patient will receive either implants with an LTT or an RBT surface according the study randomization schedule.

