12.4 Statistical Analysis

The general approach to statistical analysis of the study aims will be based on mixed-model analysis of variance (ANOVA). This approach will accommodate the inclusion of correlated observations due to study subjects potentially contributing measurements of more than one single tooth site to the analysis.

The sample distributions will be examined for each outcome variable. If these distributions depart substantially from normality, transformations of the data will be evaluated. If normality cannot be established by transformation, rank-based analyses will be used.

Subjects will be included as a random effect on the analyses that include multiple observations per subject. For analysis of histological data, only one tooth site per subject will be evaluated and the model will not include a random effect.

Smoking status will be included in all models in order to account for differences in response between smokers and non-smokers, and so that the analysis will correspond to the study's randomization strategy. Comparisons between smokers and non-smokers are not a primary interest in the study.

For aims in which interaction terms are of interest, significant interaction terms will be investigated using plots of least square means and separate post-hoc analyses for individual time points.

Hypothesis 1

Differences among the four groups will be evaluated by the overall F-test for the ANOVA. Pairwise comparisons among group means will be conducted using Tukey's test. Contrasts will be constructed to address each specific aim (SA).

SA-1: Compare alveolar ridge dimensions in grafted extraction sockets to that of sites healed without grafts after 8 weeks of post-extraction healing.

This SA will be addressed by comparing the combined mean of the three graft groups (FDBA/TCP, DDBA/TCP/PRP, FDBA/TCP/PDGF) with that of the CONTROL group by calculating a contrast and the corresponding F-test. Pairwise comparisons among means will be conducted using Tukey's test..

Hypothesis II

The addition of growth factors to bone grafting materials will enhance osseous and soft tissue healing.

SA-2: Assess the efficacy of bone grafting with and without enrichment with growth factors to preserve the volume of bone in extraction sockets.

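### Does the subject blocking variable in SA-7's Cox model make the LTT versus RBT hazard ratio impossible to estimate?

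*Combined protocol and SAP*

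**What the plan says.** Implant type is a participant-level factor. Section 4.2 states that "each participant in groups 1-4 will be further randomized into one of two implant strata". Section 4.4 adds that "Subjects with multiple sites will receive the same implant design in all study sites", and section 5.2 confirms it: "Each patient will receive either implants with an LTT or an RBT surface according the study randomization schedule".

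SA-7 in section 12.4 takes signs and symptoms of infection as its primary outcome, because implant failure is expected to be very rare. It tabulates infection frequencies by implant type and then fits a Cox model to the two types, "allowing for adjustment for potential confounding variables and covariates". Clustering gets one sentence: "A blocking variable representing the individual subject will be included in order to reflect multiple implants per study subject".

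Two general rules come earlier in section 12.4. One concerns clustering: "Subjects will be included as a random effect on the analyses that include multiple observations per subject". It also stands in the synopsis, and the only exception given with it is histology, where there is one site per subject. The other concerns the stratification factor: "Smoking status will be included in all models in order to account for differences in response between smokers and non-smokers".

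**The concern.** A block is often fitted as a stratum or as a set of fixed indicators, and the documents neither define the term nor use it anywhere else. Under either form, implant type is fully confounded with subject. The Cox model is the only inferential analysis stated for SA-7's primary outcome, so under that reading the randomized comparison of infection would have no estimate and no test, only a table of frequencies. Smoking status and extraction group, which are also fixed within a subject, would be lost with it. The random-effect rule might be thought not to help, since section 12.4 introduces it under mixed-model ANOVA while SA-7 declares a survival approach and words its own clustering instruction.

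**Working it through.** **1. The plan's own SA-7 figure.** Section 12.5 gives an odds ratio of about 3.2 at 80% power, with an effective 50 per implant group, proportions centred on 0.50 and two-sided 5% testing.

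- p2 = √3.2 / (1 + √3.2) = 0.6414; p1 = 1 − 0.6414 = 0.3586; difference = 0.2829.
- Standard error under the null = √(2 × 0.25 / 50) = 0.1000.
- Standard error under the alternative = √(2 × 0.3586 × 0.6414 / 50) = 0.0959.
- Power = Φ[(0.2829 − 1.96 × 0.1000) / 0.0959] = Φ(0.906) = 81.7%.

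The figure reproduces to within 2 points. It is a between-group chi-square with no subject block. The effective 50 per group is close to the plan's own discount for clustering: 120 sites / 1.25 = 96, or 48 per implant type.

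**2. Subject as strata.** For an event at implant i of subject s, the partial-likelihood factor is exp(βx_i) / Σ exp(βx_j), summed over that subject's implants still at risk. All of them share the value x_s, so with n at risk the factor is exp(βx_s) / [n exp(βx_s)] = 1/n. β cancels from every factor. On one simulated data set (80 subjects, 40 per type, 166 implants, 126 events) the log partial likelihood was −69.70 at β = −2, 0, 1.1 and 5, with score 0 and information 0. The software stopped with a singular matrix.

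**3. Subject as fixed indicators.** Implant type equals the sum of the indicators of the LTT subjects, up to a constant that the baseline hazard absorbs. Type, smoking and 79 subject indicators make 81 columns of rank 79. With three extraction-group dummies there are 84 columns, still of rank 79. Type and smoking add nothing to the indicators.

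**4. Subject as a random effect.** On the same data set, a Gaussian shared frailty with standard deviation fixed at 1 gave a log hazard ratio of 0.91 (SE 0.30). A marginal Cox model with subject-clustered robust variance gave 0.62 (SE 0.19). Both are estimable.

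A wider check used 1,200 simulated data sets for each form, with mean event counts from about 11 to 65 per setting. Moving the hazard ratio from 0.2 to 5 left the log partial likelihood unchanged, apart from rounding, in every data set under strata or fixed indicators. Under the frailty it changed in every data set, by at least 1.7 units. The documents give no event rate, so event rates, frailty variance and the share of smokers were assumed. Steps 2 and 3 are identities and do not depend on those assumptions.

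**5. Which form the text supports.**

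| Text | Strata or fixed indicators | Random effect |
|---|---|---|
| General rule in 12.4 and synopsis: random subject effect wherever there are multiple observations | contradicts | agrees |
| Smoking status in every model | cannot be met | met |
| SA-7 adjustment for covariates | impossible for any subject-level covariate | possible |
| SA-7 purpose: compare LTT with RBT | no estimate | estimate |
| 12.5: between-group power with a clustering discount | inconsistent | consistent |

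Every row points the same way.

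**The case for a change.** The strongest case for a change is that a specific instruction normally overrides a general one. SA-7 has its own clustering sentence, in different words, under a different class of model, and an analyst could follow it to the letter and fit a model with no answer. In addition, the two workable forms estimate different things: a shared frailty gives a subject-specific hazard ratio and a robust variance a marginal one (0.91 against 0.62 on the log scale in the illustration). An open choice could be made after the data are seen. The repair would cost one sentence.

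Part of this stands. The term is undefined, and the algebra under strata or fixed indicators is beyond dispute. But the specific sentence does not conflict with the general rule. It states a purpose, reflecting several implants per subject, and names no form; blocks are also routinely fitted as random. The smoking rule in the same section is accepted as reaching SA-7, so there is no good ground for stopping the neighbouring random-effect rule short of it. That rule also settles the choice between frailty and robust variance in favour of frailty. Finally, the wrong form announces itself with a singular fit or a dropped term, so it cannot lead to a misleading published hazard ratio.

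One limit should be stated. The frailty check held the variance at the value used to generate the data. It shows that the contrast is identifiable, not how precisely it would be estimated with few infections and about 1.5 sites per subject.

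**Conclusion.** The concern does not hold as a defect in the plan. It is true that subject strata or fixed indicators would leave zero information on LTT versus RBT, but the plan asks for neither. Its random-effect rule, its smoking rule, the stated aim of SA-7 and the power calculation all lead to an estimable between-subject comparison. SA-7 lacks a detail of model form that an analyst applying section 12.4 as a whole would supply as a shared frailty. The effect on stated figures is nil: the SA-7 power reproduces at 81.7% against 80%, and SA-8, SA-9 and the crestal-bone hypothesis do not depend on this model. The conclusion assumes that the general clustering rule covers SA-7, as its unrestricted wording indicates, and that a non-identifiable fit would be recognised as such.

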4.9 Post-Extraction Evaluations

Participants will return to clinic for oral evaluations as close to 7-days after the extraction/grafting procedure as possible and again at 14 days; sutures will be removed at the 14-day visit. An additional follow-up visit will be scheduled approximately 1-month following extractions. Healing will be closely monitored and appropriate data recorded on follow-up CRFs.

At each visit, medical history will be reviewed and any changes documented. Information regarding adverse events will be captured and recorded following IRB and Federal reporting guidelines. Eight weeks after the extractions, each study subject will be appointed for a second CBCT scan, a bone-fill biopsy and surgical placement of implants.

Table 2 – Study Procedures Visits -1 — 8

Procedures	V- (-1) Screening	V-1 Pre-Tx	V-2 EXT/ G	V-3 Week 1	V-4 Week 2	V-5 Week 4	V-6 Week 8 implant s	V-7 Week 10	V-8 Expose Implant
Consent Discussion/Obtained	X								
Medical History Review		X	X	X	X	X	X	X	X
Tx Plan Review		X							
Impressions		X							
Essix Retainer		X							
Randomized to Tx Groups		X							
Biopsy site selection		X							
Pre-Surg Antibiotics			X				X		
Pre-Surg Oral Rinse			X				X		
Tooth Extraction			X						
Tx Group Procedure			X						
Venipuncture (group 3 only)			X						
Clinical Photographs			X	X	X	X	X		X
CBCT Scan			X				X		
Periapical Radiographs							X		X
Post-Surg Instructions/Prescriptions			X				X		X
Suture Removal				X					X
AE's recorded			X	X	X	X	X	X	X
Bone Biopsy							X		
Implant Placement							X		
Implant Exposure									X

Table 3 Study Procedures Visits 9 —12

Procedures	V-9 Impressions	V-10 Final Restoration	V-11 12 month	V-12 24 month
Medical History Review	X	X	X	X
Impressions	X			
Clinical Photographs	X	X	X	X
Final Restoration Attached		X		
Periapical Radiographs		X	X	X
AE's recorded	X	X	X	X
Soft-tissue assessments			X	X
Pocket Depth Measurements			X	X
Patient Satisfaction			X	X

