6.2 Placement of the final restoration

Each implant will be restored in the conventional manner with an aesthetically pleasing single crown restoration. Restoring materials will be selected by the restoring dentist based on discretion of the dentist and individual patient needs. Prosthetic restoration of the implants will require numerous visits to the restorative dentist over a period of one to two-months. The restoring dentist will advise when additional visits are necessary. Photographs will document each step in the restoration process and of radiographs be taken of each area when the final restoration is cemented.

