8.4 Clinical Photography

Each study site will be monitored with digital photography to assess the soft tissue healing. Photographic assessment will be based on images taken at 1:1 ratio with a Nikon D-70 digital camera with a sunpack ringflash. Buccal and occlusal views will be obtained at the initial visit (prior to extraction), after completion of the grafting procedures, at 2 and 4 weeks, immediately prior to biopsy at 8-weeks, after implant insertion, at each prosthetic restorative visit, when the final restoration is attached and at four semi-annual follow-up visits.

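### SA-8 needs the soft-tissue index at final restoration, but the visit schedule lists soft-tissue assessment only at 12 and 24 months, and no text says the photographs fill the gap

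*Combined protocol and SAP*

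**What the plan says.** Section 12.4, SA-8, sets three measurement times: "The JEMPT index will be evaluated at the time of final restoration and at 12 and 24 months follow-up evaluations". It continues: "Mixed model ANOVA will be used to compare changes over time between implant types", and names the implant type by time interaction as the test of primary interest.

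In Table 3 (section 4.9) the row "Soft-tissue assessments" is marked at V-11 and V-12 and is blank at V-10, the final-restoration visit. The row "Clinical Photographs" is marked at V-9 through V-12.

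Section 6.2, on the final restoration, says "Photographs will document each step in the restoration process" and adds radiographs at cementation; it mentions no soft-tissue score. Section 7.1 lists the CRF items on soft-tissue health and contours for the 12- and 24-month visits. Section 8.4 gives the purpose of the photographs: "Each study site will be monitored with digital photography to assess the soft tissue healing". Its list of photograph times includes "at each prosthetic restorative visit, when the final restoration is attached".

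**The concern.** The analysis section and the visit schedule disagree on when the SA-8 outcome is measured. SA-8 concerns change, and change needs a starting value. The schedule supplies later values but no scored starting value.

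A clinic working from Table 3 and section 6.2 would photograph the site at V-10 and score nothing. If the index is a chairside assessment, that value cannot be obtained once the visit has passed. The planned interaction would then describe only the second year after implant placement. It would say nothing about the months just after the crown is attached.

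**Working it through.** **1. Planned times against scheduled times**

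| Source | Final restoration (V-10) | 12 months (V-11) | 24 months (V-12) |
|---|---|---|---|
| SA-8, section 12.4 | index | index | index |
| Table 3, soft-tissue row | blank | marked | marked |
| Table 3, photograph row | marked | marked | marked |
| Section 6.2 | photographs, radiographs | – | – |
| Section 7.1 CRF list | – | soft-tissue items | soft-tissue items |
| Section 8.4 | photographs | – | – |

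Section 8.4 words its follow-up photograph times differently from Table 3, so only its restoration entry is used here. The synopsis also places the assessment of soft-tissue contours at the two annual visits, and section 12.0 describes data capture at placement, 12 and 24 months. The soft-tissue row therefore supplies 2 of the 3 SA-8 times; photographs cover all 3.

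**2. Length of the interval at risk**

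Inputs: uncovering at about 4 months (mandible) or 6 months (maxilla) after placement, section 6.1; restoration over one to two months, section 6.2; first annual visit 12 months after placement, section 7.1.

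- Mandible: restoration at 4 + 1 = 5 to 4 + 2 = 6 months, leaving 12 − 6 = 6 to 12 − 5 = 7 months.
- Maxilla: restoration at 6 + 1 = 7 to 6 + 2 = 8 months, leaving 12 − 8 = 4 to 12 − 7 = 5 months.

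Overall, about 4 to 7 months separate restoration from the first scheduled soft-tissue assessment.

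**3. Effect on the test**

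Let D(R), D(12) and D(24) be the LTT minus RBT mean differences at the three times. With time as a categorical factor (an assumption, since SA-8 does not say), the planned interaction tests D(R) = D(12) = D(24). Without the first value it tests only D(12) = D(24).

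Suppose a difference δ arises between restoration and month 12 and then holds: D(R) = 0 and D(12) = D(24) = δ. The three-time interaction is non-zero. The two-time contrast is δ − δ = 0 whatever the size of δ. The average difference over the two visits, (δ + δ)/2 = δ, can still be estimated, but that is not the test SA-8 names.

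**4. The plan's power figure**

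Section 12.5 states 70% power at 0.50 sd and 80% power at 0.565 sd for SA-8. Inputs: two-sided alpha 0.05 and 50 effective observations per implant group (stated for SA-7 and applied here).

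- Normal approximation: 0.50 × √(50/2) = 2.50; Φ(2.50 − 1.96) = 70.5%. Noncentral t gives 69.7%.
- Detectable difference at 80%: (1.96 + 0.84) × √(2/50) = 0.560 sd; noncentral t gives 0.566 sd.

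Both figures reproduce. They are in units of the SD of change over time, so the scheduling gap does not alter them, but they presume that a change score can be formed.

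**The case against.** The strongest counter-argument is that this is one combined document, so the SA-8 sentence is itself an instruction to evaluate the index at final restoration. Section 8.4 assigns soft-tissue assessment to standardised buccal and occlusal photographs and schedules them at that visit. Section 7.1 also bases follow-up evaluation partly on photographic data.

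Nor is a blank cell in Table 3 strong evidence of omission. The table has no row for plaque and gingivitis scores, implant stability or prosthetic retention, all of which section 7.1 requires. Table 2 has no soft-tissue row although SA-3 analyses healing at weeks 1, 2, 4 and 8. The Manual of Procedures (Appendix E) may settle the matter but is not among the documents reviewed.

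Much of this stands. A reader might infer that the starting value is not taken, or that one of three time points is lost for every participant. The documents do not support either reading, because SA-8 asks for the measurement and the V-10 photographs may allow it to be scored.

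The argument does not close the gap. Table 3 lists photographs and soft-tissue assessments as separate rows marked at the same annual visits, which suggests two activities. Section 12.2 describes the soft-tissue response to implants as a clinical observation. Section 7.1 has a study dentist evaluate the implant area at the annual visits, whereas section 6.2 places restoration with the restoring dentist and gives no instruction to score. The index is not defined, its name is spelled differently in sections 12.4 and 12.5, and it is absent by name from the section 7.1 CRF list, so its scoring method cannot be inferred.

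**Conclusion.** The inconsistency is real and its consequence is conditional. If the index is scored at the chair and staff follow the visit schedule, SA-8 loses the first of its three times, and its key test shrinks to the 12-to-24-month change. If the index is scored from photographs, or if V-10 staff act on section 12.4, nothing is lost. The documents do not say which applies.

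The 4-to-7-month interval rests on the plan's approximate timings. A reader might also infer that SA-8 would become unanalysable; it would not, because a randomised comparison of LTT and RBT at 12 and 24 months would remain. SA-8 is one of nine aims, so this is a correction the sponsor should make, not a threat to the trial as a whole.

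**What to change.** Choose one scoring method and make every section agree with it.

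- **Chairside scoring:** mark the soft-tissue index at V-10 in Table 3, add it to section 6.2, and put it on the V-10 CRF, so that all three match SA-8.
- **Photographic scoring:** state in SA-8 that the index is scored from the V-10, V-11 and V-12 photographs. The investigators would need to confirm that the views taken are adequate for the index.

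If photographs are used for participants already past V-10, score all three times from photographs. A photographic first value followed by chairside values would confound scoring method with time, the factor that the SA-8 test relies on.

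The cost is one table mark and one CRF item in the first case, or one sentence and the work of scoring photographs in the second. Both use visits that already take place.
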